8.2.2 Device Deficiencies

Device deficiencies (related to the blood sampling kits) occurring at clinical sites will be collected on the device deficiency eCRF.

Trial clinicians will assess whether or not these *might* have led to an SAE if:

- i. suitable actions had not been taken, or
- ii. intervention had not been made, or
- iii. if circumstances had been less fortunate

If the device deficiency fulfils the reportable criteria above, then the event will be reported to SCTU using the Serious Adverse Event Report Form for assessment and onward reporting as appropriate.

Device deficiencies occurring at either WISH Lab (involving blood sample tubes) or ClearNote Health (involving the Avantect lab assay under investigation) will be recorded on a CRF outside of the RAVE database (both labs will be provided with written instructions for reporting of all safety events). Due to the design of the trial, there is no feedback loop in which a device deficiency occurring at either laboratory could lead to an SAE, and as such, clinicians will not assess these events and they will not be reported to MHRA. This is detailed in the Trial Risk Assessment.

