1.3.1 Risks and anticipated adverse device effects

ClearNote Health has established requirements for managing product risks associated with the development and commercialisation of Avantect. Risks have been graded based on severity (grade 1-5, where 1 indicates negligible and 5 indicates catastrophic) probability of occurrence (grade 1-5, where 1 indicates an improbable and 5 a frequent occurrence) and detectability (grade 1-5, where 1 indicates certainty of detection and 5 undetectable). Hazard analysis identified risks associated with collection of blood to be minimal (more details in Adverse Events section 8). With respect to the Avantect test itself, the primary risk relates to a false assay result (i.e., a false positive or a false negative result). All

Avantect “detected” cases will require an MRI (CT-scan only if MRI is contraindicated). Rare adverse events associated with MRI are described in Adverse Event Section 8.

Risks associated with the clinical performance study have been assessed in the SAFE-D Trial Risk Assessment.

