Streck® tubes will be processed to plasma within 24 hours of receipt in the WISH laboratory by trained operators and shipped at agreed frequencies as per the Laboratory Manual to ClearNote Health centralised laboratory (San Diego, California, USA). Streck plasma samples collected from patients randomised to the intervention arm will be analysed and results will be generated within 14 business days of receipt of arriving at Clearnote Health and “detected” test results will be reported to SCTU team by providing Avantect test results via an excel file and individual patient reports via secure file sharing (Safesend.soton.ac.uk). In the event of a sample failing predefined Avantect metrics, (expected failure rate is ~4%), the participant will be asked to return for a repeated draw (if the participant is still within the 28 days time frame from the original blood draw). If the failure happens at T0 and no blood could be collected while the participant is still within 6 months of diabetes diagnosis timeframe the participant will be asked to come back at T1. If the failure happens at T1 or T2 and no re-draw was performed, the participant will remain in study. For participants assigned to the control arm, samples will be kept for future potential Avantect testing and/or future research.

Lithium heparin samples will be processed according to SAFE-D specific SOP at the WISH laboratory and stored for future research within the SAFE-D study (or future ethically approved research).

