Possible	
The relationship with the use of the investigational device is weak but cannot be ruled out completely. Alternative causes are also possible (e.g. an underlying or concurrent illness/clinical condition or/and an effect of another device, drug or treatment).
 
Cases where relatedness cannot be assessed or no information has been obtained should also be classified as possible.
	Anticipated or Unanticipated Serious Adverse Device Effect (USADE or ASADE)
Probable	The relationship with the use of the investigational device seems relevant and/or the event cannot reasonably be explained by another cause, but additional information may be obtained.	Anticipated or Unanticipated Serious Adverse Device Effect (ASADE or USADE)
Causal relationship	
The serious event is associated with the investigational device or with procedures beyond reasonable doubt when:
 
 • The event is a known side effect of the product category the device belongs to or of similar devices and procedures 	Anticipated or Unanticipated Serious Adverse Device Effect (ASADE or USADE)

	
 • The event has a temporal relationship with investigational device use/application or procedures • The event involves a body-site or organ that 
 ○ The investigational device or procedures are applied to; ○ The investigational device or procedures have an effect on • The serious event follows a known response pattern to the medical device (if the response pattern is previously known) • The discontinuation of medical device application (or reduction of the level of activation/exposure) and reintroduction of its use (or increase of the level of activation/exposure) impacts on the serious event (when clinically feasible) • Other possible causes (e.g. an underlying or concurrent illness/clinical condition or/and an effect of another device, drug or treatment) have been adequately ruled out • Harm to the subject is due to error in use • The event depends on a false result given by the investigational device used for diagnosis (when applicable) 
In order to establish the non-relatedness, not all the criteria listed above might be met at the same time, depending on the type of device/procedures and the serious event.
	
--	---	--

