8.5.1.2 Device Deficiencies

All device deficiencies of an investigational device must be documented throughout the clinical investigation. These will be recorded in the trial eCRF. If they meet the reportable criteria in section 8.2.2. (and do not meet the exceptions listed in 8.2.2.), these will also be reported as serious adverse events using the process in section 8.5.1.3 below.

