8.6.4 WISH Laboratory and ClearNote Health laboratory

Each laboratory is responsible for:

1. Recording any device deficiencies occurring at their respective laboratories onto a CRF and sharing these with SCTU on an ad-hoc basis (at least quarterly) as requested for onward reporting to MHRA within the required timelines.

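### Section 8.2.2 exempts every laboratory device deficiency from clinical assessment and MHRA reporting on a premise that is untrue for intervention-arm detected results and conflicts with sections 8.6.3, 8.6.4 and 8.5.1.2

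*Protocol*

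**What the plan says.** Section 8.2.2 treats deficiencies differently by where they occur. Blood-kit deficiencies at clinical sites are assessed by trial clinicians for their potential to have caused a serious event, and those that qualify follow the SAE route.

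Deficiencies at the WISH laboratory, and those at "ClearNote Health (involving the Avantect lab assay under investigation) will be recorded on a CRF outside of the RAVE database", are handled separately. The reason given is that "there is no feedback loop in which a device deficiency occurring at either laboratory could lead to an SAE". The consequence drawn is that "clinicians will not assess these events and they will not be reported to MHRA". The Trial Risk Assessment is cited for detail.

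Other sections bear on the same events:

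- Section 1.3.1, on the test itself: "the primary risk relates to a false assay result (i.e., a false positive or a false negative result".
- Section 8.3, among the criteria for a causal relationship: "The event depends on a false result given by the investigational device used for diagnosis (when applicable".
- Section 8.5.1.2: "All device deficiencies of an investigational device must be documented throughout the clinical investigation. These will be recorded in the trial eCRF".
- Section 8.6.4 makes each laboratory responsible for recording its deficiencies and for "sharing these with SCTU on an ad-hoc basis (at least quarterly) as requested for onward reporting to MHRA within the required timelines".
- Section 8.6.3, item 5, has SCTU report device deficiencies to the MHRA on the manufacturer's behalf and names no laboratory exception.

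**The concern.** The investigational device is the laboratory assay. Section 8.2.2 gives clinical review to faults in the collection kit and none to faults in the assay or its processing, although the protocol places the main test risk in a false assay result. If an assay or laboratory fault lies behind a detected result that has been issued, nobody is asked whether it could have caused serious harm, and 8.2.2 keeps it from the MHRA. Laboratory and SCTU staff also face instructions on recording and onward reporting that cannot all be followed as written.

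**Working it through.** No power, alpha or sample-size figure is involved. The check sets the sections side by side.

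**1. Is there a route from the laboratory back to the participant?** Section 6.1 says of intervention-arm plasma that "results will be generated within 14 business days of receipt of arriving at Clearnote Health", with detected results then sent to SCTU. Under 7.8.1 the participant and GP are told, and an urgent suspected-cancer referral for pancreas MRI (CT if MRI is contraindicated) is arranged. The recommended MRI sequences in Appendix I include a gadolinium contrast phase. Section 8.2.1 lists contrast reactions, including acute kidney injury, and provides for listed events that turn out to be serious. So the chain from faulty detected result to referral, imaging and possible serious reaction is part of the design.

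**2. Does the safety framework recognise that route?** Yes. Section 1.3.1 names the false result as the primary risk of the test. Section 8.1 counts a false result as an adverse event when inappropriate management follows from it, and includes device malfunction among the causes of adverse events. Section 8.3 accepts a false result as a causal link.

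**3. Where does the premise hold?** Control-arm samples are stored and not tested for the trial analysis. Samples without adequate cfDNA produce a QNS report and an invitation to redraw (7.8.3). Results that are not detected are not disclosed (7.8.2). For these the premise is sounder, but 8.2.2 applies it to both laboratories without limit.

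**4. Do the recording and reporting rules agree?**

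| Question | 8.2.2 | Elsewhere |
|---|---|---|
| Do laboratory deficiencies reach the MHRA? | No | 8.6.4: shared with SCTU for that purpose. 8.6.3 item 5: SCTU reports device deficiencies, no laboratory exception |
| Where are they recorded? | On a CRF outside RAVE | 8.5.1.2: in the trial eCRF |
| Does a clinician assess their potential for serious harm? | Site kit faults yes, laboratory faults no | 8.5.1.2 and 8.5.1.3 defer to 8.2.2 |

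The first two rows conflict. In the third, the other sections follow 8.2.2, so the exemption carries through. Item 5 of 8.6.3 is the weaker of the two MHRA conflicts, because it can be read as covering only deficiencies already reported. Section 8.6.4 is specific to the laboratories.

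**5. What is still caught?** All serious adverse events are reportable whether or not related (8.2.3), within the window in 8.5.1.4. A doctor assesses causality (8.3). Deviations at the processing or analysis laboratories go to SCTU immediately (10.2.1). What remains uncovered is the deficiency as such, where a fault could have caused serious harm but no SAE has been reported. Section 10.2.1 does not close this. It covers non-compliance with the protocol, GCP or the manual of procedures, so a reagent or software fault with every procedure followed need not be a deviation. Its output is corrective action, not an assessment of potential for serious harm.

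**6. Scale.** Section 9.2 expects 7,312 − 73 = 7,239 intervention-arm per-protocol participants without pancreatic cancer. At 95% specificity, 7,239 × 0.05 ≈ 362 of them have a detected result. Adding the 48 true positives gives 48 + 362 = 410 participants whose result is to be acted on. The 362 are ordinary test error and not deficiencies. The 410 show only how many participants pass through the return route that 8.2.2 says is absent.

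**The case against.** The strongest defence is that 8.2.2 exempts the deficiency record and not the harm. Any serious event is still reported, assessed by a doctor with dependence on a false result as a criterion, and sent to the MHRA. A sample swap or contamination would usually be a procedural deviation that reaches SCTU at once under 10.2.1, and quarterly sharing in 8.6.4 is a minimum. This stands, and it confines the gap to the assessment of the fault itself.

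Sections 8.2.2 and 8.6.4 may also be meant to work together, with 8.2.2 excluding individual reports and 8.6.4 feeding the quarterly summaries of 8.8. That is plausible, but 8.2.2 does not say so, and it would not repair the premise. The Trial Risk Assessment may give a fuller rationale. It is not among the documents, so it could not be checked, and a cross-reference does not resolve conflicting protocol text.

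A reader might infer more than the documents support:

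- **Biopsy or surgery because of a laboratory error.** A detected result leads to imaging. With normal imaging the participant continues study visits (7.9.1), and further work-up follows abnormal imaging under the local team (7.9.2, 7.9.4). The direct exposure is referral and imaging.
- **Harm through a wrong result of not detected.** These results are not disclosed, and 8.1 requires a management decision based on the false result.
- **A full contradiction with 8.5.1.2.** Its reporting clause allows for the 8.2.2 exceptions. Only the place of recording conflicts.
- **Wrong results entering sensitivity and specificity unmarked.** The laboratories record the events and share them with SCTU, and flagging in the dataset can be left to the SAP or data management.

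**Conclusion.** The point holds in a limited form. The statement that no laboratory deficiency could lead to an SAE is wrong for intervention-arm detected results, and the exemption built on it is therefore too wide. Section 8.2.2 also conflicts with 8.6.4, and on its face with 8.6.3 item 5, on whether these deficiencies reach the MHRA, and with 8.5.1.2 on where they are recorded.

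The practical gap is one missing step: a fault behind an issued detected result is not put to the test that a faulty collection kit at a site must pass. The documents give no deficiency rate, so the number of affected results cannot be estimated. The conclusion does not depend on that number. It assumes only that a laboratory or assay fault can sometimes produce a wrong detected result, which is consistent with the protocol's own definition of a device deficiency and its statement of the main test risk. As a stated safety rule that is incorrect as written and cheap to correct, it should be amended.

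**What to change.** 1. In 8.2.2, remove the unlimited statement and confine the exemption to laboratory deficiencies that cannot affect an issued or pending intervention-arm result, for example those involving untested control samples.
2. Have the CI or delegate assess laboratory deficiencies that could have produced a wrong intervention-arm result against the criteria already in 8.2.2 for site deficiencies. Report those that qualify through the existing 8.5.1.3 process and within its 3-day limit.
3. Reconcile 8.2.2, 8.5.1.2, 8.6.3 and 8.6.4 on two matters: whether laboratory deficiencies are recorded in the eCRF or on a separate CRF, and whether they reach the MHRA individually, through the quarterly summary, or both according to type.
4. Bring the laboratories' written instructions and the Trial Risk Assessment into line.

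The cost is protocol wording, an update to those two supporting documents, and a small extra review workload for the CI and SCTU. The laboratories already record the events, so no new data collection is needed.

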8.2.3 Seriousness

A complete assessment of the seriousness must always be assessed by a medically qualified doctor who is registered on the delegation of responsibility log; this is usually the investigator.

All adverse events (whether related to study procedures or not) that fulfil the criteria definition of 'serious' in section 8.1, must be reported to SCTU using the Serious Adverse Event Report Form.

8.2.4 Exceptions

For the purposes of this trial, the following **SAEs do not** require reporting to SCTU using the Serious Adverse Event Report Form:

- Hospitalisations for elective treatment of a pre-existing condition (the pre-existing condition needs to have been captured within the selected pre-existing conditions of interest CRF and/or the patient's medical notes).

8.3 CAUSALITY

A complete assessment of the causality must always be made by a medically qualified doctor who is registered on the delegation of responsibility log; this is usually the investigator.

If any doubt about the causality exists, the local investigator should inform SCTU who will notify the Chief Investigator. Other clinicians may be asked for advice in these cases.

In the case of discrepant views on causality, SCTU will classify the event as per the worst-case classification and if onward reporting is required, the MHRA and/or Research Ethics Committee (REC) will be informed of both parties' points of view.

Relationship	Description	Denoted
Not related	
Relationship to the device or procedures can be excluded when:
 
 • The event is not a known side effect of the product category the device belongs to, or of similar devices and procedures • The event has no temporal relationship with the use of the investigational device or the procedures • The event does not follow a known response pattern to the medical device, and is biologically implausible • The discontinuation of medical device application (or the reduction of the level of activation/exposure [when clinically feasible]) and reintroduction of its use (or increase the level of activation/exposure), do not impact on the serious event • The event involves a body-site or an organ not expected to be affected by the device or procedure • The serious event can be attributed to another cause (e.g. an underlying or concurrent illness/clinical condition, an effect of another device, drug, treatment or other risk factors) • The event does not depend on a false result given by the investigational device used for diagnosis, when applicable • Harms to the subject are not clearly due to use error 
In order to establish the non-relatedness, not all the criteria listed above might be met at the same time, depending on the type of device/procedures and the serious event.
	SAE
Unlikely	The relationship with the use of the device seems not relevant and/or the event can be reasonably explained by another cause, but additional information may be obtained	SAE
Possible	
The relationship with the use of the investigational device is weak but cannot be ruled out completely. Alternative causes are also possible (e.g. an underlying or concurrent illness/clinical condition or/and an effect of another device, drug or treatment).
 
Cases where relatedness cannot be assessed or no information has been obtained should also be classified as possible.
	Anticipated or Unanticipated Serious Adverse Device Effect (USADE or ASADE)
Probable	The relationship with the use of the investigational device seems relevant and/or the event cannot reasonably be explained by another cause, but additional information may be obtained.	Anticipated or Unanticipated Serious Adverse Device Effect (ASADE or USADE)
Causal relationship	
The serious event is associated with the investigational device or with procedures beyond reasonable doubt when:
 
 • The event is a known side effect of the product category the device belongs to or of similar devices and procedures 	Anticipated or Unanticipated Serious Adverse Device Effect (ASADE or USADE)

	
 • The event has a temporal relationship with investigational device use/application or procedures • The event involves a body-site or organ that 
 ○ The investigational device or procedures are applied to; ○ The investigational device or procedures have an effect on • The serious event follows a known response pattern to the medical device (if the response pattern is previously known) • The discontinuation of medical device application (or reduction of the level of activation/exposure) and reintroduction of its use (or increase of the level of activation/exposure) impacts on the serious event (when clinically feasible) • Other possible causes (e.g. an underlying or concurrent illness/clinical condition or/and an effect of another device, drug or treatment) have been adequately ruled out • Harm to the subject is due to error in use • The event depends on a false result given by the investigational device used for diagnosis (when applicable) 
In order to establish the non-relatedness, not all the criteria listed above might be met at the same time, depending on the type of device/procedures and the serious event.
	
--	---	--

8.4 EXPECTEDNESS

There are no adverse events that are expected to meet the definition criteria for seriousness; therefore all **serious** adverse events will be ‘unexpected’.

The nature and/or severity of the event should be considered when making the assessment of expectedness. If these factors are not consistent with the current information available, then the AE or device deficiency should be recorded as ‘unexpected’.

8.5 REPORTING PROCEDURES

Any questions concerning adverse event reporting should be directed to the SCTU in the first instance. Sites at which participant blood samples are collected, as well as both labs (WISH Lab and ClearNote Health) will receive written instructions and a tailored flow chart to assist in reporting procedures of all safety events.

8.5.1 Reporting Details

8.5.1.1 Adverse Events

All AEs should be recorded in the patient's medical notes, and all related AEs (Adverse Device Effects - ADEs) should be reported in the trial eCRF as per the trial specific requirements listed in Section 8.2.

8.5.1.2 Device Deficiencies

All device deficiencies of an investigational device must be documented throughout the clinical investigation. These will be recorded in the trial eCRF. If they meet the reportable criteria in section 8.2.2. (and do not meet the exceptions listed in 8.2.2.), these will also be reported as serious adverse events using the process in section 8.5.1.3 below.

8.5.1.3 Serious Adverse Events

For all reportable SAEs and device deficiencies, an SAE report form should be completed with as much detail as possible (including any relevant anonymised treatment forms and/or investigation reports) and emailed to SCTU immediately but at least within 3 days of site becoming aware of the event.

Or

Contact SCTU by phone for advice and then email a scanned copy of the SAE report form completed as above.

SAE REPORTING CONTACT DETAILS

*Please email a copy of the SAE form to
SCTU within 3 days of becoming aware of the event*

Email: [contact]

FAO: Quality and Regulatory Team

For further assistance: [contact] (Mon to Fri 09:00 – 17:00)

The event term should be the most appropriate medical term or concept (which the SCTU will code to MedDRA) and grades given in accordance with the National Cancer Institute (NCI) CTCAE v5.

Additional information should be provided as soon as possible as it is received if all information was not included at the time of reporting.

As per regulatory and local SCTU procedures, all SAEs and device deficiencies that might have led to an SAE as detailed in section 8.2.2 will be reported to the MHRA. Additionally, SAEs will be reported to the REC, if the event was:

- 'Related' – i.e., resulted from the administration of any of the research procedures;

and

- ‘Unexpected’ – i.e., an event that is not listed in the CPSP as an expected occurrence.

